Study Design	
Overall Study Design
 
This is an open-label, dose escalation study to evaluate the safety, PK, biodistribution, dosimetry, and tumor targeting potential of SNA002 in patients with solid tumors.
 
This study will consist of Screening Period, Baseline Period, Study Period and Safety Follow-up Period. A signed and dated informed consent form will be obtained before any study-related procedures are performed. Collect CT/MRI/PET/CT results from subjects within one month before screening to obtain baseline tumor assessment. Eligible patients will be enrolled at least two days before the administration of study drug. The radiation dose for all dose groups at the time of administration should be ranged from 37 to 200MBq. Four dose levels of NOTA-SNA002 are planned: 0.1mg, 0.3mg, 0.5mg and 0.9mg. The final drug product administered to the patient is [⁶⁸Ga]Ga-NOTA-SNA002. Three to seven patients will be sequentially enrolled into each dose cohort. Patients will be administered a single dose of SNA002 over 1 minute as an intravenous bolus. Patients will be observed for 6±1h and 24±6h post infusion for infusion-related and other adverse reactions. In the first cohort of patients, whole body imaging will be acquired using PET/CT at 15±5 minutes, 60±10 minutes and 120±20 minutes post-injection. Before each imaging, the patients need to empty bladder as much as possible. Total-body PET-CT scans can be performed on 1-2 subjects in a certain dose group or each dose group, covering at least one of the aforementioned time points. In the subsequent cohorts,

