6.1.7.2 Dose Escalation Schedule

The dose escalation is determined through both imaging results and safety results:

Imaging:

The Imaging Reviewer Committee consisted of the principal investigator and nuclear medicine physicians.

- 1) If the first three positive tumor lesions in a certain dose group judged by the IRC having a high image quality (such as $\text{T}/\text{B} > 1.5$, etc.), it can be decided from the imaging perspective to increase to the next dose group after continuing to enroll 3-4 cases in this dose group, or directly increase to the next dose group for further exploration;
→If the quality of the first 3 cases in the subsequent dose group is comparable to that in the previous dose group, the IRC shall discuss whether to discontinue further enrollment from a

imaging perspective (e.g. The image quality of the first 3 cases in the 0.3mg dose group is similar to that in the 0.1mg dose group, then stop recruiting, and the 0.1mg dose was identified as the optimal image dose).

- If the quality of the first 3 cases in the posterior dose group is higher than prior, another 3 to 4 cases will be enrolled. After the completion of the posterior dose group, the IRC will discuss and decide whether this group should not be explored from the imaging aspect (e.g. The image quality of the first 3 cases in the 0.3mg dose group is higher than that in the 0.1mg dose group, then 3-4 cases , and the subsequent dose exploration was not carried out, and the 0.3mg dose was identified as the optimal image dose).

- 2) If the first three positive tumor lesions in a certain dose group judged by IRC present poor imaging quality (such as $T/B \leq 1$) or nonvisualization (functional imaging without nuclides), the decision of stopping enroll in this dose group can be made from an imaging perspective, and the dose group can directly increase to the next or second dose group (for example, if the imaging quality of the 0.1mg dose group is poor in three consecutive cases, the dose group can increase to the 0.3mg or 0.5mg dose group);
- 3) If the last dose group shows nonvisualization of the positive tumor lesions determined by the IRC in the first three cases, discussion will be conducted to determine whether to adjust the subsequent dose from the imaging perspective or terminate the entire clinical trial.

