8) Develop a plan for obtaining target lesion specimens (if applicable): Determine whether to collect tissue specimens after administration based on specific circumstances. If the subject has obtained a biopsy specimen within 2 weeks prior to enrollment and has obtained/can undergo immunohistochemical PD-L1 detection results (such as PD-L1 immunohistochemical detection of pathological tissues in different directions of the lesion collected through bronchoscopy within 2 weeks prior to enrollment), and no treatment has been given, no further biopsy is required. Otherwise, pathological specimens need to be collected in this clinical study. The collection method can accept biopsy or surgical resection of specimens, which is determined by the investigators based on the subject's situation.
 (note: the investigators can arrange for the subjects to enter a safe follow-up period after the subjects complete the tissue specimen collection (D2) or surgical specimen collection (D2-D5) during the trial period, or after the subjects who do not need to collect tissue specimens again complete all operations in D1, in order to shorten the waiting time for subsequent treatment from an ethical perspective).

9) Vital signs: Vital signs are evaluated at 6 ± 1 h after administration on D1.

10) Examination of injection site: observe injection site for redness, swelling, heat, pain, itching and other symptoms 6 ± 1 h after administration.

11) Record concomitant medications.

12) Record AEs.

D2 to D5

- 1) Target lesion specimen acquisition: Biopsy specimens can include endoscopic (such as gastroscopy, fiberoptic bronchoscopy, laparoscopy, etc.) and puncture biopsy specimens, which are generally conducted in D2. The preferred specimen for collection is the primary tumor lesion or metastatic lesion with the highest SUVmax; The collection principle is to collect at least one biopsy sample from the target tumor lesions that can be collected, and the maximum number of samples for the same patient is 5. Ideally, biopsies should be performed on both positive and negative lesions of the same patient under PET imaging. The location of specimen collection and the selected collection method will be determined by the investigators based on previous imaging results and the PET results of this experiment. Perform PD-L1 immunohistochemical detection after obtaining target tissue samples.

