10.4.2 Analysis of The Primary Efficacy Endpoints

Pharmacokinetic evaluation

- Change in whole blood radiation dose: Blood samples are collected on D1 after administration and the ^{68}Ga dose in blood samples is measured using a radiation detector.
- Change in serum radiation dose: Blood samples are collected on D1 after administration and the whole blood samples are treated to obtain serum. The ^{68}Ga dose in serum is measured using a radiation detector.
- SNA002 detection: Blood samples are collected on D1 after administration for the detection of SNA002 in blood samples in the central laboratory.
- Hemodynamic change of SNA002: Imaging results are interpreted and the heart is delineated as ROI. Data collected at various time points are analyzed, and the result is determined according to the concentration–time curve.
- Change in urine sample radiation dose: Urine samples should be collected before and post administration. ^{68}Ga dose in urine sample should be measured with γ detector.

Evaluation of imaging features

- Evaluation of PET imaging features of target tumor tissues: In combination with CT, the image results were read, multiple target tumor lesions were selected (no less than 1, ideally, no less than 1 should be selected for both positive and negative imaging foci), the uptake of $[^{68}\text{Ga}]$ Ga-NOTA-SNA002 in each target tumor lesion was observed, and the count was recorded, quantization for SUV-based standardized uptake (SUV_{max}, SUV_{mean} etc.).
- Tumor lesion hot spots by PET imaging——target to background ratio: Hot spot and T/B ratio is determined based on the SUV_{mean} (semi-quantitative analysis) of the target lesion and the lesion contralateral side and liver.
- Evaluation of optimal imaging time: The optimal imaging time is determined based on the T/B ratios at different time points.
- Optimal dosage: should be determined according to T/B ratio, detection ability of lesions (primary lesions, metastatic lymph nodes and distant metastases) and normal organs with abundant PD-L1 expression except lesions are fully inhibited.

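### Section 10.4.2 lets tracer uptake on the study PET decide which lesions are analysed; the target lesions should be listed from baseline imaging first.

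*Combined protocol and SAP*

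**What the plan says.** The first imaging bullet of Section 10.4.2 gives an order of work: "In combination with CT, the image results were read, multiple target tumor lesions were selected". The number and kind of lesion follow in brackets: "no less than 1, ideally, no less than 1 should be selected for both positive and negative imaging foci". The firm requirement is one lesion. Having both a positive and a negative focus is a preference, and no maximum is set. Section 10.4.2 does not define positive or negative, but the parallel biopsy rule in Section 7.3.3 ties the pair to the trial's own scan: "Ideally, biopsies should be performed on both positive and negative lesions of the same patient under PET imaging".

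SUV and T/B are then taken from the target lesions. On timing: "The optimal imaging time is determined based on the T/B ratios at different time points". On the optimal dose: "should be determined according to T/B ratio, detection ability of lesions (primary lesions, metastatic lymph nodes and distant metastases", together with a condition on normal organs.

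Lesion information that does not depend on the tracer is already collected. The Protocol Summary (Study Design) says: "Collect CT/MRI/PET/CT results from subjects within one month before screening to obtain baseline tumor assessment". Inclusion criterion 5 in Section 5.1 requires at least one lesion on prior imaging that can be biopsied. No section uses this imaging to fix the target lesions or their number, and none says how several lesions in one patient are summarised.

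**The concern.** Uptake is what the imaging analysis sets out to measure. If the reader sees uptake first and then picks lesions partly because they are hot or cold, the analysed set depends on the result.

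Two things can follow. If the hotter lesions are picked, T/B is overstated. If one hot and one cold lesion are picked in each patient, the analysed mix moves towards half and half whatever the dose, and dose groups can look more alike than they are.

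PET imaging characteristics, the optimal dose and the optimal imaging window are stated secondary objectives, judged on groups of 3 to 7 patients. In groups of that size, one or two discretionary lesion choices can change the picture.

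**Working it through.** **Figures in the plan.** The plan gives no number for this step. The nearest design figure reproduces: 4 dose groups × 3 to 7 patients = 12 to 28 (Section 10.5). Lesions per patient, the spread of T/B and an expected dose effect are not stated, so what follows is an illustration.

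**Assumptions.** K = 2, 3 or 5 lesions per patient. Log T/B is normal, with SD w = 0.4–0.6 within patients and b = 0–0.4 between patients. A lesion is positive at T/B > 1.5 (the escalation rule's example of high image quality, Section 6.1.7.2; Section 10.4.2 gives no cut-off). The true positive share p is 0.40 at one dose and 0.70 at another. The reader keeps one positive and one negative lesion where both exist, otherwise one lesion.

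**Positive share, b = 0 (exact).**
- Pooled over lesions: A/(A + B), with A = 1 − (1 − p)^K and B = 1 − p^K.
- Averaged within patient first: ½[1 + p^K − (1 − p)^K].

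K = 2:
- Pooled: 0.64/1.48 = 0.432 and 0.91/1.42 = 0.641, a difference of 21 points.
- Within patient: 0.40 and 0.70, a difference of 30 points.

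K = 3:
- Pooled: 0.784/1.720 = 0.456 and 0.973/1.630 = 0.597, a difference of 14 points.
- Within patient: 0.424 and 0.658, a difference of 23 points.

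K = 5:
- Pooled: 0.922/1.912 = 0.482 and 0.998/1.830 = 0.545, a difference of 6 points.
- Within patient: 0.466 and 0.583, a difference of 12 points.

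**Full range, b up to 0.4 (simulation).** True difference 30 points:

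| Lesions per patient | Pooled | Averaged within patient |
|---|---|---|
| 2 | 21–23 | 30 |
| 3 | 14–19 | 23–28 |
| 5 | 6–14 | 12–23 |

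Pooling loses more because patients with mixed lesions contribute two lesions and the others one.

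**T/B ratio between doses.** The true ratio is exp[σ(z₀.₇₀ − z₀.₄₀)] = exp(0.777σ), with σ = √(w² + b²).
- w = 0.4, b = 0: exp(0.311) = 1.36. Pooled selection gives about 1.29 with 2 lesions and 1.17 with 5.
- w = 0.6, b = 0.4: σ = 0.721, ratio 1.75. Pooled selection gives about 1.57 and 1.38.

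**Hottest lesion only.** The geometric mean T/B is multiplied by exp(w·e), where e is the expected maximum of K standard normal values (0.564 for K = 2, 1.163 for K = 5).
- K = 2: exp(0.4 × 0.564) = 1.25 to exp(0.6 × 0.564) = 1.40.
- K = 5: exp(0.4 × 1.163) = 1.59 to exp(0.6 × 1.163) = 2.01.

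The level is therefore overstated by 25–40% or 59–101%. The factor is the same at both doses, so it cancels from their ratio.

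**A second set of assumptions.** Geometric mean T/B 1.2 versus 1.8 (ratio 1.50), log-SDs of 0.2 or 0.4 within and between patients, cut-off 1.0 or 1.5, averaged within patient. The share of the log difference kept is 100% with 2 lesions, 82–102% with 4 and 59–105% with 8. In the worst case the ratio falls to 1.27, and a true change in positive share from 0.31 to 0.66 appears as 0.43 to 0.55. At the other end the ratio is slightly inflated, to 1.53.

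**The case against.** The strongest reply is that the text sets floors. The positive/negative pair is only a preference, nothing caps the number of lesions and none has to be dropped. A reader who measures every lesion complies fully and introduces no bias. The trial is exploratory, descriptive and small, and Section 10.1 promises a formal SAP in which a lesion rule could be set.

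Much of this stands, and it rules out several stronger readings that a reader might infer:

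- *The plan imposes a one-positive, one-negative quota.* It does not. The illustration shows what the preference does if it is followed and nothing more is measured.
- *Dose differences are necessarily blurred.* The loss is nil with one lesion. With two lesions it depends on an unstated choice between pooling and averaging. In some settings it is slightly reversed.
- *Taking the hottest lesion distorts the dose comparison.* Under the model it raises the T/B level and leaves the ratio unchanged. Section 10.4.2 does not call for the hottest lesion; a highest-SUVmax preference appears only for biopsy, in Section 7.3.3 and the notes to Table 4.
- *Detection ability is counted only in the selected lesions.* Section 10.4.2 does not say so. The detection figures apply only if it is done that way.
- *Scan time is biased in the same way.* T/B is compared across time points, naturally within the same lesions, so the between-dose mechanism does not carry over directly.
- *The optimal dose rests on these T/B values alone.* It also uses detection ability, a normal-organ criterion and the imaging committee's review. The escalation rule, which begins "If the first three positive tumor lesions in a certain dose group judged by", is a separate matter.

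What the reply does not remove is the order of work. Lesions are chosen after uptake is seen, with uptake as a stated aim of the choice. Leaving the choice open does not protect it from the result. Nor does the absence of a hypothesis test, because a descriptive summary of selected lesions can still misdescribe a dose group. A SAP due only before database lock may be written after the study scans have been read for escalation.

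**Conclusion.** The point holds as a cheap improvement. Section 10.4.2 allows tracer uptake to decide which lesions supply SUV and T/B, and nothing elsewhere fixes them from the baseline imaging. This can misstate T/B levels, and it can blur dose differences where patients have several mixed lesions.

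The size cannot be derived from the documents. Under the stated assumptions, a true 30-point difference shrinks to between 6 and 23 points if lesions are pooled. If they are averaged within patient it stays at 30 with 2 lesions and falls to between 12 and 28 with 3 or 5. Those results require one positive and one negative lesion to be kept per patient and the rest discarded, which the text permits but does not require. With a single lesion, or if all lesions are measured, there is no bias.

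**What to change.** Replace the selection wording in the first imaging bullet of Section 10.4.2 with text to this effect:

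> Target lesions are listed from the baseline CT, MRI or PET/CT before the study PET is opened, by a rule that does not use tracer uptake (for example, the largest lesions up to a set number, including the primary where present). SUVmax, SUVmean and T/B are measured in every listed lesion at every scan, whether or not it is visible, using the CT outline where needed. Values are summarised within patient before dose groups are compared. Detection is the number of listed lesions seen divided by the number listed. Lesions seen only on the study PET are reported separately.

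Keep the positive/negative pairing for the choice of biopsy sites only.

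The cost is a change of wording and a short listing and outlining step on images already collected; no extra scan or patient is needed. T/B figures may look less favourable, because lesions with little uptake will count.

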10.4.3 Analysis of the Secondary Endpoints

Immunogenicity evaluation

- Anti-SNA002 antibody: ADA blood samples are collected before administration and on D6 \pm 1d and D28 \pm 2d after administration for the detection of anti-SNA002 antibody in the independent third-party central laboratory.

Evaluation of correlation of expression between imaging and IHC

- The IHC analysis is conducted to the collected tumor tissue samples (tested by the independent third party central laboratory) and the results are compared with those of imaging. Take the immunohistochemistry result as the true values (if only baseline immunohistochemistry result is available, the baseline result is the true value; if both baseline and post administration immunohistochemistry results are available, then post administration results are true values) .Sensitivity [true positive/(true positive + false negative)], specificity [true negative/(true negative + false positive)], positive predictive value [true positive/(true positive + false positive)], and negative predictive value [true negative/(true negative + false negative)] are calculated. Explore the correlation between PET imaging features (such as tumor SUVs, tumor/muscle SUVs) and immunohistochemical results.

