7.3 Study Schedule

7.3.1 Screening

D - 14 to D - 2

- Sign the ICF.
- PD-L1 immunohistochemistry results.
- Collect demographic data.

- 4) Inquire and record medical history (including personal history, past history, allergy history, and cancer history).
- 5) Tumor stage.
- 6) Pathological test results within 1 year before screening.
- 7) Vital signs.
- 8) Physical examination.
- 9) 12-lead ECG.
- 10) Cardiac function score: scored according to NYHA standards
- 11) ECOG score.
- 12) Chest x-ray (not required if chest CT results are available).
- 13) Enhanced CT/enhanced MRI/PET-CT (results of examinations conducted at the study site or other tertiary hospitals within 30 days prior to enrollment are acceptable).
- 14) Laboratory tests: blood routine, blood biochemistry, electrolyte, coagulation function, urine routine, serum virology, thyroid function tests, and serum pregnancy test (only for female subjects of childbearing age). Serum virology can accept results within 28 days before screening, while other laboratory tests can accept results within 7 days before screening.
- 15) Review compliance with inclusion/exclusion criteria.
- 16) Record concomitant medications.

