7.3.7 Schedule of Events Table

Table 4 Schedule of Events Table

Study Period/Visits	Screening Period	Baseline Period	Study Period (5 days)		Safety Follow-up Period (D6-28)		Premature Withdrawal ¹⁸
Study Day (s)	D-14~2	D-1	D1	D2~D5	D6±1d	D28±2d	
Informed consent	x						
Inclusion/exclusion criteria	x	x					

Study Period/Visits	Screening Period	Baseline Period	Study Period (5 days)		Safety Follow-up Period (D6-28)		Premature Withdrawal ¹⁸
Study Day (s)	D-14~2	D-1	D1	D2~D5	D6±1d	D28±2d	
Demographics	x						
Physical examination	x			x			
Vital signs ¹	x		x	x			x
Medical history:	Personal history	x					
	Past history	x					
	Allergy history	x					
	Tumor History	x					
Tumor stage	x						
Pathological examination ²	x						
Laboratory examination ³	Blood routine	x			x		x
	Blood Biochemistry	x			x		x
	Electrolyte	x			x		x
	Thyroid Function	x					
	Coagulation Function	x			x		x
	Urinalysis	x					
	Blood Pregnancy (If Needed)	x					
	Serum Virology	x					
12-lead ECG	x				x		x
Cardiac function score	x						
Physical condition score	x						
Chest X-ray (can be ignored if there is chest CT) ⁴	x						
CT/MRI/PET-CT ⁵	x						
Administration							
[⁶⁸ Ga]Ga-NOTA-SNA002 administration ⁶			x				
Biological Samples, Imaging, Safety Data, Specimen Collection							
Blood sampling ⁷			x				
Urine sampling ⁸			x				
Ada ⁹			x		x	x	x
Pet-ct ¹⁰			x				
Measurement of radiation dose ¹¹			x				
Formulate a Plan for Obtaining Target Lesion Specimens (If Performed) ¹²			x				
Collection of tissue samples from target lesions (if performed) ¹³				x			
Pd-111 immunohistochemical examination ¹⁴	x			x			
Other							
Examination of injection site ¹⁵			x	x			
Enrollment ¹⁶		x					
Out of group						x	
Concomitant medications ¹⁷	x	x	x	x	x		x

Study Period/Visits	Screening Period	Baseline Period	Study Period (5 days)		Safety Follow-up Period (D6-28)		Premature Withdrawal ¹⁸
Study Day (s)	D-14~2	D-1	D1	D2~D5	D6±1d	D28±2d	
Ac ¹⁸			x	x		x	x
Distribute/recycle journal cards						x	

1. Vital Signs: tested during the screening period, 6 ± 1 hours after D1 administration, and 6 ± 2 hours after D2 biopsy (if performed).
2. Pathological Examination: if the pathological examination results within one year before screening are obtained, and the subject receives biopsy samples within two weeks before enrollment and has not undergone chemotherapy, radiotherapy, or immunotherapy until enrollment, biopsy may not be performed after administration in this clinical trial.

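### Section 10.4.3 accepts a lone baseline PD-L1 IHC result as the truth without the conditions that Section 7.3.3 sets for relying on pre-dose tissue

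*Combined protocol and SAP*

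**What the plan says.** Section 10.4.3 takes IHC as the true value for sensitivity, specificity, PPV and NPV. Where baseline and post-dose results both exist, the post-dose result is used. Otherwise, "if only baseline immunohistochemistry result is available, the baseline result is the true value". Nothing is said there about the age of the baseline specimen, the lesion it came from or treatment since it was taken.

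Section 7.3.3, D1 item 8, decides when pre-dose tissue is good enough to skip a new biopsy. It begins: "If the subject has obtained a biopsy specimen within 2 weeks prior to enrollment and has obtained/can undergo immunohistochemical PD-L1 detection results". It then adds that no treatment may have been given. If these conditions are not met: "Otherwise, pathological specimens need to be collected in this clinical study". Note 2 to Table 4 (Section 7.3.7) gives a similar waiver for a patient with a specimen from the last two weeks who "has not undergone chemotherapy, radiotherapy, or immunotherapy until enrollment, biopsy may not be performed after administration in this clinical trial".

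The screening list in Section 7.3.1 limits the age of most results. Pathology: "Pathological test results within 1 year before screening". Imaging: "results of examinations conducted at the study site or other tertiary hospitals within 30 days prior to enrollment are acceptable". Laboratory tests: "Serum virology can accept results within 28 days before screening, while other laboratory tests can accept results within 7 days before screening". The entry "PD-L1 immunohistochemistry results" has no limit.

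**The concern.** The protocol has a collection rule and an analysis rule for the same question, namely when pre-dose tissue can stand for PD-L1 status at the time of the scan. Only the collection rule has limits. A patient whose old tissue does not satisfy item 8, and whose required new specimen then fails, still enters the accuracy table with the old result as truth.

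The protocol itself shows why this matters. Table 3 in Section 2.2 lists, as a weakness of IHC, that PD-L1 readings are easily altered by earlier treatment, and that a section speaks only for the tissue examined. Inclusion criterion 3 admits patients at relapse or under treatment. Suppose IHC was done on a diagnostic specimen 10 months ago, chemotherapy followed, and the post-dose biopsy cannot be evaluated. A PET scan that shows current PD-L1 status correctly could then count as a false positive or false negative. The four measures serve the exploratory objective on positive and negative predictive efficacy.

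**Working it through.** **Sample size.** Four dose levels with 3 to 7 patients each: 4 × 3 = 12 and 4 × 7 = 28. This reproduces the planned 12-28 (Section 10.5).

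**Time from tissue to PET on D1.**
- Post-dose specimen, D2 to D5 (Section 7.3.3): 1 to 4 days.
- Specimen meeting item 8, with enrolment on D-1 (Section 7.3.2): at most 14 + 1 = 15 days.
- Screening IHC done on pathology tissue one year before screening at D-14: 365 + 14 = 379 days. Section 10.4.3 does not exclude this. One year is about 26 times the 2-week window (365/14).

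**How a lone baseline outside item 8 can arise.** Item 8 requires new tissue when its conditions fail. But it also leaves the decision on post-dose collection to the circumstances of the case, and Table 4 marks tissue collection as conditional. A biopsy can also fail or prove inadequate after dosing. Section 10.4.3 then uses the baseline result by default.

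**Effect on the estimates.** None of the following inputs is in the documents; all are assumptions. Let f be the share of patients with such a result, d the chance that the IHC label no longer holds (independent of PET), Se and Sp the true PET sensitivity and specificity, and p the share PD-L1 positive.

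At p = 0.5 a fraction f × d of each labelled group is wrongly labelled, so

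observed Se = (1 − fd) × Se + fd × (1 − Sp), and the loss is f × d × (Se + Sp − 1). The loss in specificity is the same.

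One affected patient, Se = Sp = 0.90 (factor 0.80):
- 1 of 28, d = 0.10: 0.80 × 0.10/28 = 0.003, or 0.3 points.
- 1 of 12, d = 0.30: 0.80 × 0.30/12 = 0.020, or 2.0 points.

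With Se = Sp = 0.85 (factor 0.70) the range is 0.70 × 0.10/28 = 0.25 points to 0.70 × 0.30/12 = 1.75 points. At p = 0.5 the loss is proportional to the number of affected patients.

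Prevalence matters. At p = 0.3,

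observed Se = [(1−f)pSe + f(p(1−d)Se + (1−p)d(1−Sp))] / [(1−f)p + f(p(1−d) + (1−p)d)].

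For one patient with Se = Sp = 0.90:
- 1 of 28, d = 0.10: 0.2693/0.3014 = 0.893, a loss of 0.7 points.
- 1 of 12, d = 0.30: 0.265/0.310 = 0.855, a loss of 4.5 points.

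**Comparison with sampling error.** With 6 to 14 IHC-positive patients (half of 12 to 28), the standard error of a 90% sensitivity is √(0.9 × 0.1/6) = 0.122 to √(0.9 × 0.1/14) = 0.080, or about 12 to 8 points.

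**The case against.** Read as a whole, the protocol closes most of the gap. By design, a patient has only a baseline result when the item 8 waiver applies, so the fallback in 10.4.3 reads naturally as the analysis counterpart of that waiver. Inclusion 5 requires a lesion that can be biopsied, and exclusion 1 removes patients who cannot undergo biopsy. Inclusion 4 limits pathology results to one year, a plausible outer bound even though it does not name PD-L1 IHC. The same bullet in 10.4.3 says that collected tissue is tested centrally, although it does not say whether this covers the site's screening result. No hypothesis is tested (Section 10.2), the accuracy measures are not among the endpoints in Section 4.2, and Section 10.1 promises a formal SAP before database lock.

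Most of this stands, and it limits the weight of the point. It does not remove the residual case: eligibility criteria cannot prevent a failed biopsy, and for that case 10.4.3 gives a positive instruction rather than staying silent.

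A reader might infer two stronger points.
- That Table 4 notes 2 and 12 open a second gap, because they waive the biopsy without tying the IHC result to the recent specimen. They are better read as shorthand for item 8, which states the IHC condition.
- That the accuracy estimates could be badly distorted. If 25-50% of patients were affected and d were 10-30%, the loss at p = 0.5 would run from 0.25 × 0.10 × 0.80 = 2 points to 0.50 × 0.30 × 0.80 = 12 points. At p = 0.3 sensitivity could fall to 0.24/0.36 = 0.667, a loss of 23 points. Nothing in the documents supports shares of that size, and following item 8 should keep the share small.

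**Conclusion.** The analysis rule is looser than the protocol's own collection rule, and in a narrow case it can label a correct PET read as wrong. That case is a required post-dose specimen that is missing or not evaluable, with the only IHC older, pre-treatment or from another lesion. The documents do not show how many patients this will involve; with none, the effect is nil. For one patient the expected loss is about 0.3 to 2 points in sensitivity and in specificity, given 50% prevalence, 90% accuracy and a 10-30% chance of changed status. At 30% prevalence the sensitivity loss is 0.7 to 4.5 points. Either range is below the sampling error of the estimates. These are average shifts; in the actual table a label is either right or wrong. Only an exploratory objective is affected. The point merits a cheap improvement, not a redesign.

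**What to change.** In Section 10.4.3, or in the formal SAP that Section 10.1 promises:
- Use a lone baseline result as the true value only if the IHC was done on a specimen taken within 2 weeks before enrolment, with no anticancer treatment between specimen and dosing.
- List other baseline-only subjects separately, and report sensitivity, specificity, PPV and NPV with and without them.
- In Section 7.3.1, item 2, record the specimen date, the lesion sampled and any intervening therapy, brought up to date at dosing.

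The treatment limit is worded as treatment after the specimen on purpose. Item 8 does not say over what period it counts treatment. Read strictly, it would drop a patient under treatment who has a fresh specimen, although inclusion 3 admits such patients. Pointing Table 4 notes 2 and 12 to item 8 would be tidy but is editorial.

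The cost is three data fields and a slightly smaller denominator in an exploratory accuracy table. No visit, scan or biopsy is added, and the subjects concerned stay in all other analyses. The rule should be fixed before PET and IHC results are compared, so that nobody chooses afterwards which baseline results count as truth.
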